2.0 BACKGROUND

Hepatocellular carcinoma (HCC) is the third ranked cause of global cancer mortality. There is an increasing incidence of HCC in the United States over the last twenty years, largely due to the Hepatitis C epidemic but increasingly related as well to nonalcoholic fatty liver disease (1,2). For patients with single HCC and compensated liver disease (normal liver function and no portal hypertension), partial liver resection (LR) is the preferred treatment, although there is significant risk of recurrence. For patients

HCC who are Barcelona-Clinic Liver Cancer (BCLC) class A (1 lesion < 5cm, or 2-3 lesions all < 3cm) and who, due to decreased liver function, are not candidates for LR, liver transplantation (LT) is the treatment of choice. The current median waiting time in New York, however, is greater than 12 months, creating the risk of dropout due to tumor progression (currently estimated to be around 20-25%). In order to mitigate this risk, patients listed for LT typically undergo locoregional therapy with transarterial chemoembolization (TACE) and/or thermal ablation (TA) as a bridge to LT (3,4). However, only 30% of patients are candidates for curative treatments (5).

Patients with BCLC A HCC who due to age, medical, or psychosocial issues are not candidates for LR or LT are typically treated with TA, which has the potential to completely destroy tumor nodules. Recent studies in selected patients demonstrated equivalent or improved rates of overall survival and recurrence-free survival between TA and surgical resection (6-8). TA is often used in combination with TACE, which both aids in accurately targeting TA and may augment the extent of resultant tissue ablation. One recent randomized study showed improvements in both overall survival and recurrence-free survival in patients receiving TA + TACE compared with TA alone (9). Application of TA is limited to tumors < 4cm, and as the performance of TA requires accurate placement of a needle probe into the tumor, nodules situated in inaccessible locations or adjacent to vital structures are not amenable to treatment. Patients with tumors beyond Milan criteria but confined to the liver and without macrovascular invasion (BCLC B) who are not candidates for resection are typically treated with TACE, which prolongs survival but does not offer hope of cure (10-11).

For lesions that are not candidates for TACE and/or TA, stereotactic body radiation therapy (SBRT) has recently been shown to be an effective tool in the locoregional treatment of HCC. SBRT is a specific application of intensity modulated radiation therapy (IMRT) in which very high doses of radiation are delivered in fewer fractions to a small target. SBRT has the potential to widen the therapeutic index by delivering a much higher equivalent dose, standardized by the concept of Biological Effective Dose (BED), which measures the true biologic dose as a function of dose per fraction, total dose, and a tissue's inherent radiosensitivity (12). SBRT employs the use of image guidance, usually with iterative CT imaging moments before the radiation is delivered, with real-time fusions by the radiation oncologist of the planned treatment volume with the patient's anatomy at the time of each treatment. By utilizing SBRT, the tumor receives a very large dose of radiation while minimizing the exposure of adjacent healthy tissue, enabling clinically effective and safe radiation delivery for HCC (13-22).

There are several unique advantages of SBRT over traditional TACE with or without TA as well. To start, SBRT can be used to treat lesions adjacent to or invading vasculature which might not be a candidate for TACE or TA. While there are anatomic limitations to SBRT, these are different than other local therapies broadening the spectrum of local treatments. SBRT is also non-invasive with a relatively low toxicity profile. It can be used in combination with or adjunctive to other local therapies. This benefit might be further potentiated based on the different mechanism of action of SBRT vs. TACE and/or TA. Finally, SBRT can be used to treat larger lesions than RFA which is generally restricted to lesions less than 4 cm.

Preliminary series have demonstrated encouraging results using SBRT for the treatment of HCC. Phase I and II data from the Princess Margaret Hospital evaluated the efficacy and safety of 6-fraction SBRT to a median dose of 36 Gy in Child-Turcotte-Pugh (CTP) class A patients with HCC not suitable for surgery.

TACE, RFA, or ethanol ablation (23-24). Results demonstrated treatment to be well tolerated, with no classic radiation-induced liver damage (RILD) observed. 23-29% of the patients experienced a transient progression from CTP class A to B, the vast majority of which resolved by 12 months. One year local control was 87%. Other groups have demonstrated comparable safety and control, even in Child B patients, with 2 year local control rates, as defined as no progression in the treated lesion after treatment, of 90% (25). A clear dose response relationship has been established demonstrating that doses greater than 30 Gy in 6 fractions have better local control (24). Of note, delayed tumor necrosis, despite relative persistent in size, has been documented following SBRT of HCC (26).

SBRT has also been incorporated into locoregional treatment of HCC following TACE. In 50 patients who received a median of 2 TACEs prior to receiving SBRT (median dose 57 Gy in 3 fractions), a 2-year local control rate of 94.6% was achieved (27). Treatment was well tolerated with no classic RILD observed. 12.8% of patients progressed from CTP class A to B. 8.5% of patients developed ascites with normal alkaline phosphatase levels. Of note, at these high doses, 6.4% and 4.3% of patients had grade 3 or grade 4 GI toxicity, respectively. This study focuses on a heterogeneous population as well as high radiation doses resulting in higher than expected grade 3 toxicity.

The assessment of treatment response after TACE and TA is currently based on loss of internal vascularity on contrast-enhanced imaging as outlined in the mRECIST criteria. The response to radiotherapy, however, may not be as accurately assessed by mRECIST. Diffusion-weighted imaging (DWI) and uptake by hepatocytes of liver-specific contrast (Gd-EOB-DTPA) are potentially complementary methods to assess hepatocyte damage. The use of DWI has been reported in the diagnosis of liver tumors and for the evaluation of treatment response in liver metastases (treated with systemic chemotherapy) and HCC (treated with TACE) (28-34). Most studies have observed an early rise in Apparent Diffusion Coefficient (ADC) values concomitant with devascularization, with subsequent decrease in ADC values in HCC (35). A recent study successfully correlated radiographic changes on the hepatobiliary phase of Gd-EOB-DTPA-enhanced MRI with a threshold dose of radiation 3 months after SBRT (36). In their study of 50 patients undergoing SBRT for HCC, Sanuki et al proposed a threshold dose of 30 Gy for CTP class A and 25 Gy for CTP class B patients. They demonstrated that the highly irradiated area surrounded by these isodose curves on the treatment planning scan corresponded to the region of focal liver reaction identified on Gd-EOB-DTPA-enhanced MRI.

3.0 PARTICIPANT SELECTION

All patients will be evaluated in the multidisciplinary Liver Tumor Board where eligibility criteria, entry, and disease parameters will be evaluated and documented. In addition, all patients are required to consult with a radiation oncologist, interventional radiologist, and medical oncologist before starting the study. Subjects who enroll in this study must have a single HCC > 3 cm and not be candidate for upfront surgical resection. Patients must not have had any prior radiation to the thorax or abdomen. Potential patients will be screened based on their past medical history, radiological scans, blood work, competing clinical trials, transplant eligibility, and overall ability to comply with the protocol.

3.1 Inclusion Criteria

Participants must meet the following criteria to be eligible to participate in the study:

3.1.1 Participants must be diagnosed with HCC either pathologically or by the American Association for the Study of Liver Diseases (AASLD) radiographic criteria (Bruix Hepatology 2011). The criteria specifies CT or MRI intense arterial uptake followed by “washout” of contrast in the venous-delayed phases. Any atypical lesions must be confirmed by biopsy.

3.1.2 A single liver lesion with tumor size ≥ 3 cm as defined as maximal diameter in the axial dimension on MRI. Included in the measurement are both enhancing and non-enhancing components of the lesion.

3.1.3 Maximum tumor size of 7 cm as defined as maximal diameter in the axial dimension on MRI.

3.1.4 Age ≥ 18 years

3.1.5 Child-Pugh class A or B7 without ascites

3.1.6 ECOG score 0

3.1.7 No prior treatment of current HCC. However, recurrent HCC after resection may be included.

3.1.8 Ability to understand and the willingness to sign a written informed consent document.

3.2 Exclusion Criteria:

Participants will be excluded from participation in the study if they have any of the following exclusionary criteria:

3.2.1 Pregnancy which will be assessed via pregnancy test prior to TACE and repeated prior to SBRT.

3.2.2 Metastatic disease outside of the liver

3.2.3 Vascular invasion as evidenced by vessel occlusion or radiographic evidence of tumor thrombus.

3.2.4 Contraindications to MRI, including claustrophobia, metallic implants, and pacemakers

3.2.5 Tumor for which adequate radiation dosage cannot be safely delivered (see dose constraints below)

3.2.6 Prior therapeutic radiation therapy to the abdomen and/or lower thorax as defined as below the carina to the pelvic inlet.

3.2.7 Inability to provide informed consent based on persistent lack of understanding, inability to find adequate translation, impaired mental status such as mental retardation, drug induced, or traumatic brain injury.

3.2.8 Multiple liver tumors making the patient a BCLC Stage B

3.2.9 Prior treatment, except for surgical resection, to the lesion being targeted in the protocol.

4.0 DELIVERY OF TACE

4.1 Initial TACE will be delivered per standard protocol

4.2 After 3 to 8 weeks following the intial TACE, patients will return for labwork and consideration for a second TACE to the same site. TACE will not be repeated if the bilirubin is > 3 ng/mL.

4.3 Prior to preceding to radiation therapy, the patient will have labwork done including CBC and LFTs to assess return to within grade 2 elevations of baseline labwork prior to proceeding onto radiation.

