1.0 INTRODUCTION

1.1 Study Design

This is a non-randomized pilot study to assess the objective response rate and durability of response of combination Trans-Arterial Chemoembolization (TACE) with immediate stereotactic body radiation therapy (SBRT) in the treatment of unresectable hepatocellular carcinoma (HCC). Eligible patients will be selected based on having a lesion greater than 3 cm which would make them ineligible for other local therapies such as TACE and thermal ablation (TA). Eligible, consented, and registered patients will be treated with two sessions of standard TACE with ethiodol separated by a 4-week interval. After ensuring adequate return to baseline liver function, the patients will then be treated with SBRT to the targeted lesion to 30-40 Gy in 5 fractions. Tumor response will be assessed using mRECIST criteria as well diffusion weight imaging (DWI) via Magnetic Resonance Imaging (MRI) surveillance. In addition, tolerability and toxicity will be recorded via CTCAE v. 5.0. The essential hypothesis of this study is that combination TACE and SBRT for > 3 cm HCC will produce higher response rates and durable control compared to historical controls of TACE alone.

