5.6 Timing of Radiation

5.6.1 The first radiation treatment should begin within 7 days of the second TACE. Acceptable variation would be within 21 days of completion of TACE.

5.6.2 Per protocol, all external beam radiation treatments should be delivered within 15 calendar days. An acceptable variation is 16-21 calendar days. Treatment requiring greater than 22 calendar days constitutes a major protocol variation.

5.7 PTV coverage: The intent is for the prescription dose to cover 95% of the PTV. The PTV should be treated to as high a dose as possible, respecting normal tissue constraints, as a dose response has been observed. Modifying a PTV due to close proximity of adjacent OARs is not permitted. An acceptable variation per protocol would be 90-95% PTV coverage.

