6.0 DATA COLLECTION

6.1 Before enrollment, patients will be interviewed and assessed for meeting inclusion and exclusion criteria. Patients will also be assessed for ability to complete the protocol and follow up. Follow up and data collection will proceed as outlined below and summarized in Appendix D.

6.1.1 Pretreatment data will include the following parameters:

1. Demographics: age, sex, etiology of liver disease
2. Past Medical History: comorbidities
3. Related symptomatology
4. Performance status according to ECOG
5. Liver and renal function tests: bilirubin, AST, ALT, albumin, alkaline phosphatase, GGTP, BUN, creatinine, Na, INR, and platelet count
6. Serum alpha fetoprotein (AFP)
7. Tumor MRI with Gd-EOB metrics: size, number of tumors, tumor location, tumor necrosis, mean ADC of whole tumor and viable component
8. Liver MRI metrics: degree of hepatobiliary phase enhancement, mean ADC
9. Chest CT

6.2 A regular on treatment visit (OTV) will be used to assess acute treatment related toxicity according to CTCAE v. 4. In the event that there is a treatment break, patients will be seen at least once a week.

6.3 Three to 6 weeks following completion of SBRT, the patient will be seen in routine follow up to assess and manage any post-treatment complications. At that time of the first visit, blood work will be obtained as follows:

Liver and renal function tests: bilirubin, AST, ALT, albumin, alkaline phosphatase, GGTP, BUN, creatinine, Na, INR, and platelet count
 Serum alpha fetoprotein (AFP)

6.4 Routine follow up will be scheduled every 3 to 4 months from the completion of radiation (2 to 3 months after the initial one month visit). For medical necessity, patients can be sooner. In addition to assessment of toxicity according to CTCAE, blood work will be obtained as follows:

Liver and renal function tests: bilirubin, AST, ALT, albumin, alkaline phosphatase, GGTP, BUN, creatinine, Na, INR, and platelet count
 Serum alpha fetoprotein (AFP)

6.5 Every 3 to 4 months post-radiation, the patient will have an MRI with Gd-EOB-DTPA to assess tumor response (as outlined below) up to one year.

6.6 Every 6 to 8 months, the patient will have a CT of the chest, abdomen, and pelvis to assess for systemic disease. If clinically warranted, imaging can be obtained sooner. PET/CT might be used if clinically warranted.

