8.0 STATISTICAL ANALYSES

8.1 Sample Size

In March 2020, we increased our target enrollment goal from 30 patients to 40 patients. A more recent systematic review with data from more than 10,000 patients with HCC undergoing TACE found that the objective response rate (ORR) was 52.5%¹ which is greater than the ORR of 35% assumed in our original sample size calculation. If we assume the proposed treatment regimen of TACE+SBRT to be ineffective in this patient population if the ORR is less than 52% and continue to consider the proposed treatment regimen effective if it can improve the ORR to at least 75%, then increasing the sample size to 40 patients yields 82% power with a type I error rate of 0.05 to detect an ORR >75% using a two-sided exact test for one proportion.

Study treatment will consist of three parts: a TACE, followed by another TACE after one month, followed in approximately 2 weeks by 5 radiation treatments given every other day. After the treatments, the subject will be followed with clinical exams, blood work, and MRIs approximately every three months up to one year. The full duration of a participant's time on study is 14 months. A timeline of the treatment is as follows:

The overall study timeline will be approximately 7 years to completion, resulting in publication. The study was initially IRB approved on 11/18/2014 with a target enrollment of 17 patients. The modification to increase the target enrollment to 30 patients was IRB approved on 11/8/2016 in the continuation submission. The 30th patient was enrolled on 11/19/2019. Primary analyses are being done as of this submission and we anticipate having a preliminary manuscript submitted by May 2020. With the additional enrollment goal, there will likely be subsequent analyses after the initial publication. The additional 10 patients will be enrolled in the next 12-18 months and will be used to strengthen the study results. With this additional enrollment and study timeline extension, we anticipate enrollment to close by mid-2021 and the study to close by early 2022 or become a phase II trial.

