Appendix D: Protocol Timeline and Required Interventions/ Studies

Time point	Activities
Enrollment	
 • Screening for eligibility • Consultation with Radiation Oncology • Consultation with Interventional Oncology • Consultation with Medical Oncology • History and physical including ECOG performance status • Baseline renal and liver function tests • Baseline chemistry and CBC • Baseline AFP • Baseline MRI with Eovist of the liver • Baseline CT of the chest
Study initiation – time “0”	
 • TACE #1
3 to 8 weeks post TACE #1	
 • Renal and liver function tests • TACE #2 • Simulation for SBRT
1 to 3 weeks post TACE #2	
 • Renal and liver function tests • SBRT
3 to 6 weeks post SBRT	
 • Follow up history and physical • Renal and liver function tests • AFP
3 to 4 months post SBRT	
 • Follow up history and physical • Renal and liver function tests • AFP • MRI with Eovist of the liver
6 to 7 months post SBRT	
 • Follow up history and physical • Renal and liver function tests • AFP • MRI with Eovist of the liver • CT of the chest
9 to 10 months post SBRT	
 • Follow up history and physical • Renal and liver function tests • AFP • MRI with Eovist of the liver
12 to 13 months post SBRT	
 • Follow up appointment

	
• Renal and liver function tests• AFP• MRI with Eovist of the liver• CT of the chest
14 months and beyond post SBRT	
• Follow up per standard of care

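### The bilirubin limit for withholding the second TACE is printed in the wrong unit: 3 ng/mL is 0.0003 mg/dL, a value every patient would exceed

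*Combined protocol and SAP*

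**What the plan says.** Section 4.2 governs the step between the two chemoembolizations. Three to eight weeks after the first, "patients will return for labwork and consideration for a second TACE to the same site", and the rule that follows is: "TACE will not be repeated if the bilirubin is > 3 ng/mL".

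The rest of the plan treats the second session as routine:

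- Section 1.1 describes "two sessions of standard TACE with ethiodol separated by a 4-week interval".
- Section 5.6.1 times radiation from it: "The first radiation treatment should begin within 7 days of the second TACE".
- Section 8.1 summarises treatment as "a TACE, followed by another TACE after one month", then radiation.
- Appendix D schedules the second TACE at 3 to 8 weeks and places SBRT at "1 to 3 weeks post TACE #2".

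Bilirubin also appears in the laboratory lists of section 6.0 ("Liver and renal function tests: bilirubin, AST, ALT, albumin" and further tests), with no unit and no limit.

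**The concern.** A limit that decides whether a patient receives a planned treatment has to separate patients who should go on from patients who should not. At 3 ng/mL it separates no one, because any realistic serum bilirubin lies above it. Followed as printed, section 4.2 would cancel the second TACE for everyone and so contradict the regimen the trial was set up to study.

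A conditional stop rule is not itself at odds with a two-session plan, since some patients may properly stop after one. The only defect is that the printed condition is always true.

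Two things are at stake. The first is clarity for the treating team, because this is the only stated laboratory criterion for repeating a liver-directed procedure in patients with Child-Pugh A or B7 disease (section 3.1.5). The second is auditability. Section 9.3 asks that departures from the protocol be avoided unless there is an immediate hazard, yet on the printed text every second TACE is a departure. Nobody checking against that text could tell a proper repeat from an improper one.

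**Working it through.** **Inputs**

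- Printed limit: 3 ng/mL (section 4.2).
- Serum bilirubin in the enrolled population: not given anywhere in the documents. I assume 0.1 to 3 mg/dL and show the ends and one value between.
- Population: Child-Pugh A or B7 without ascites (section 3.1.5), so there is no reason to expect unusually low bilirubin.

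The limit is a stated threshold, not a derived figure, so there is no calculation in the plan to reproduce. The check is a unit conversion.

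**Step 1: convert the printed limit**

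1 mg/dL = 1,000,000 ng / 100 mL = 10,000 ng/mL.

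3 ng/mL ÷ 10,000 = 0.0003 mg/dL.

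**Step 2: compare with the assumed range**

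Multiple of the limit = (bilirubin in mg/dL × 10,000) ÷ 3.

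| Assumed bilirubin (mg/dL) | In ng/mL | Multiple of printed limit |
|---|---|---|
| 0.1 | 1,000 | 333 |
| 1 | 10,000 | 3,333 |
| 3 | 30,000 | 10,000 |

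Even at the bottom of the range the patient is more than two orders of magnitude over the limit, so the conclusion does not depend on the exact range chosen.

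**Step 3: which unit was meant?**

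If mg/dL was intended, the limit is 30,000 ng/mL and the printed value is too low by a factor of 30,000 ÷ 3 = 10,000. Changing only ng to mg does not repair the text: 3 mg/mL × 100 mL/dL = 300 mg/dL, a limit that would effectively never stop anyone. The replacement unit therefore needs to be confirmed and written out.

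**Step 4: does another section correct it?**

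- Section 6.0 lists bilirubin without a unit.
- Appendix D lists renal and liver function tests before the second TACE without a threshold.
- Section 4.3 and the table in 5.9.1 set hepatic conditions for radiation, not for TACE.

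None supplies a bilirubin unit or a limit for repeating TACE.

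**Step 5: does it reach the statistics?**

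The sample size in section 8.1 rests on 40 patients and response rates of 52% and 75%. Bilirubin does not enter it, nor the binomial test in section 8.2.

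**The case against.** The strongest reply is that this is a slip in a unit label that nobody would act on. Section 4.2 itself offers a second TACE for consideration, which would be pointless if the rule always forbade it, and four other places plan that session. Any clinician would see that the literal limit cannot be meant, and the larger the discrepancy, the less likely it is to be applied. By the time of section 8.1 the 30th patient had been enrolled, and the text gives no sign that the regimen had been blocked. Liver safety also has other supports: the Child-Pugh entry limit, the laboratory recovery required by 4.3 before radiation, and the hold rules in 5.9.1. On this view the point is editorial.

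Much of that stands. The practical effect is probably small, the literal error is over-restrictive and not hazardous, and the multiples in the table show how implausible the literal reading is, not any harm to the trial. It is also true that mg/dL is inferred.

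It does not remove the point. The line is current, operative text that decides whether a treatment is given, and it is wrong as written. The other hepatic safeguards act at entry or before and during radiation, and none replaces a limit for repeating TACE. The rule was also still in use: section 8.1 planned 10 further patients, with enrollment expected to close by mid-2021.

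**Conclusion.** The concern holds. The limit in section 4.2 equals 0.0003 mg/dL, about 333 to 10,000 times below an assumed serum bilirubin range of 0.1 to 3 mg/dL, and no other section repairs it. The conversion is exact. The only assumptions are that range, to which the conclusion is not sensitive, and the intended unit of mg/dL, on which the factor of 10,000 depends. Nothing in the documents suggests that the number 3 is wrong or that any patient lost a second session because of this. It should be fixed because it is a treatment threshold; it is not a threat to the trial's inference.

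**What to change.** Amend section 4.2 to correct the unit only, most plausibly so that the second TACE is withheld when bilirubin exceeds 3 mg/dL. The investigators should confirm that unit before the text is changed, because the documents state no other unit for bilirubin.

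The cost is a one-line correction at the next amendment, with no change to sample size, power, analysis or visit schedule.
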